12.4 Masking

All site personnel will be masked to the treatment assignment for each subject. Specific aspects of the trial design are intended to optimize the integrity of the masking and all staff will be trained to the procedures for masking during the site initiation visit.

In addition to those procedures, each Investigator will be provided with individually sealed and numbered envelopes, corresponding to subject randomization numbers. In the case of an emergency, an envelope may be opened to identify the TMS treatment assignment for a particular subject. In all circumstances, the Investigator will notify Neuronetics prior to unmasking the TMS treatment for any subject, if possible. In the event that the emergency circumstances preclude first notifying Neuronetics immediately, the Investigator should contact Neuronetics within one business day and provide the reason(s) for unmasking and date of opening of the envelope must be documented in the subject's files.

The unmasking must also be documented on the Adverse Event page of the CRF, and in the subject's source documents. Additionally, the Investigator must submit a written explanation describing the unmasking within 5 working days. All other randomization envelopes must be returned unopened to Neuronetics at the completion of the trial.

13 Preparation and Administration of Investigational Device

Administration of TMS treatment will be consistent with procedures outlined in the NeuroStar[®] User Manual and User training documentation.

13.1 Motor Threshold Determination Procedure – per NeuroStar User Manual

Subjects in Phase I randomized to active treatments will receive treatment parameters that have been safely and feasibly utilized in adult randomized, controlled trials and in the 2011 Wall et al. open-label trial in adolescents. Stimulation will occur at a maximum of 120% magnetic field intensity relative to the subject's resting motor threshold (MT), at 10 pulses per second (10 Hz) for 4 seconds, with an intertrain interval of 26 seconds. During the treatment for the first week only, the intensity of the magnetic field can be reduced, as needed, to 110% for tolerability. Upward titration with goal of return to maximum

Page 34 of 61

intensity (not to exceed 120% MT) will occur as tolerated by each subject by the end of the first week of treatment. Treatment sessions will last for 37.5 minutes (75 trains) to provide a total of 3,000 pulses per treatment session. Up to a total of 30 treatments will be completed within 6 weeks of treatment initiation.

13.2 Treatment

Subjects in Phase I randomized to sham treatments will have identical schedules, systematic assessments, and a treatment approach to active treatment. Neither the subject nor Investigators will know whether the treatment is active or sham in nature. The sham coil will be identical in its appearance to the active coil. Furthermore, Neuronetics, Inc. has created an acoustic matching profile that renders the "sound" of the treatments virtually indistinguishable to subjects or researchers. The acoustic signal creates a painless percussive sensation that will be felt by the subject and will assist in simulating the active condition.

Subjects in Phase II will receive treatment that is identical in schedule and parameters to that of Phase I with the exception that the known-active therapy coil will be used for all treatments. Up to a total of 30 treatments will be completed within 6 weeks.

Subjects in Phase III will be monitored for symptom re-emergence. In the event that the subject's CGI-S score worsens by 1 point or more from the value observed at Phase III entry, then the subject must be rescheduled for repeat clinical assessment within 1 week. If this symptom change is confirmed at that visit, then the subject is considered to have met criteria for clinical deterioration. TMS re-introduction treatment should occur with the known active coil using the same protocol parameters. A Motor Threshold determination must also be performed immediately prior to administration of the first TMS treatment to a subject in any TMS treatment block. During each active TMS retreatment block, subjects are assessed every other week with the same efficacy measures used in the Week 6 visit and the C-SSRS. During a TMS retreatment block, TMS should be discontinued when the CGI-S score has returned to the value observed at Phase III entry. Subjects must be withdrawn from the study if they meet criteria for relapse as defined:

- Meeting diagnostic criteria for major depression, confirmed on two occasions within a two week period, or
- Failure to experience symptomatic improvement by restoration of CGI-S score to its Phase III entry value upon the completion of an TMS retreatment block

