See Appendix C for schedule of events.

Outcome measures for Follow up Phase III, including HAMD/MADRS structured interview, QIDS-A17-SR, CDRS-R, and CGI-S, will be assessed per schedule of events.

Page 27 of 61

Subjects will be evaluated clinically for adverse events at each visit and at the bi-weekly phone call. The bi-weekly calls are done as a safety check to assess worsening of illness between monthly visits. The phone call will be documented as a progress note and placed with the subjects' source documentation. SAEs will be recorded as they occur and reported to Neuronetics by the study site within one business day of notification.

The C-SSRS will be completed weekly during TMS retreatment session(s). The YMRS will be completed if the interval assessment of spontaneous adverse events indicates the potential occurrence of symptoms of mania or hypomania. In addition, in all subjects receiving TMS retreatment, air conduction thresholds will be assessed for both left and right ears at baseline and at the end of the retreatment block.

Vital signs (including height, weight, blood pressure and heart rate), cognitive function assessments and air conduction thresholds for both ears will be assessed at the end of six-month follow-up.

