Motor Threshold Determination ^k							
TMS Retreatment ^{,c,,e,l} (5x/week for 6 weeks)							
See protocol text for description of retreatment parameters							

a. An Informed Consent/Assent for this study must be signed prior to initiating any study-related procedures.

b. Subjects who prematurely discontinue should complete all Month 6 procedures within 2 days after their last TMS treatment session.

c. TMS retreatments should begin on a Monday, with daily treatment sessions occurring on Monday through Friday of each week. All efficacy and safety assessments must be completed prior to the start of retreatment. Efficacy assessments must be completed every other week during each TMS retreatment with the assessment beings conducted after the last treatment for the two week block. TMS treatment to stop when the CGI-S value returns to the Phase III entry score or a full 6 weeks of TMS treatment has been completed. A 3 week taper should follow each retreatment session. TMS retreatment can occur multiple times if symptom re-emergence occurs.

- d. Y-MRS to be completed if symptom indicating mania occurs. If positive, a M.I.N.I./M.I.N.I. KID must be repeated to determine if subject meets full DSM-5 criteria for mania or hypomania. If positive, subject to be discontinued from the study and followed clinically.
- e. C-SSRS to be performed after last TMS retreatment session on last day of the retreatment week.
- f. Performed on a subset of subjects at participating sites.
- g. Audiometry assessments must be performed immediately prior to the start of the TMS retreatment and at the completion of the retreatment course.
- h. Efficacy assessments to be performed the end of each month for monthly visits. Subjects will be called to assess safety and well-being between visits at approximately 2 weeks post previous months visit.
- i. Those AEs occurring following informed consent signature through 30 days after the last study visit will be collected.
- j. Medication treatment for emergent insomnia and emergent anxiety is permitted (refer to protocol for usage allowance).
- k. A Motor Threshold Determination (MT) is to be performed prior to the administration of the first TMS treatment in each treatment course. In addition, motor threshold may be repeated at any time during the course of the active TMS treatment sessions based on clinical assessment of the supervising physician.

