#### Phase III:

Phase				Month m follow up		
Timepoint	Month 1	Month 2	Month 3	Month 4	Month 5	Month 6/ET b
Day(s)	Taper-30	Day 60	Day 90	Day 120	Day 150	Day 180
Informed Consent/Assent	Xa					
Efficacy Assessments c,h						
HAMD 24 /MADRS			x			x
CDRS-R			x			x
CGI-S	х	x	x	х	х	x
QIDS-A17-SR	х	х	x	х	х	x
Neuropsychological Assessments						
NIH Toolbox Cognition Battery						x
Safety Assessments						
Vital Signs						x
YMRS d						
C-SSRS e						
Structural MRI f						x
Audiometry Assessment g						х
Adverse Events h,i	X					Х
Concomitant Treatment h,j	X					Х
Motor Threshold Determination k						
TMS Retreatment ,c, ,e,l (5x/week for 6 weeks)						
See protocol text for description of retreatment parameters						

a. An Informed Consent/Assent for this study must be signed prior to initiating any study-related procedures.

- b. Subjects who prematurely discontinue should complete all Month 6 procedures within 2 days after their last TMS treatment session.
- c. TMS retreatments should begin on a Monday, with daily treatment sessions occurring on Monday through Friday of each week. All efficacy and safety assessments must be completed prior to the start of retreatment. Efficacy assessments must be completed every other week during each TMS retreatment with the assessment beings conducted after the last treatment for the two-week block. TMS treatment to stop when the CGI-S value returns to the Phase III entry score or a full 6 weeks of TMS treatment has been completed. A 3-week taper should follow each retreatment session. TMS retreatment can occur multiple times if symptom re-emergence occurs.
- d. Y-MRS to be completed if symptom indicating mania occurs. If positive, a M.I.N.I./M.I.N.I. KID must be repeated to determine if subject meets full DSM-5 criteria for mania or hypomania. If positive, subject to be discontinued from the study and followed clinically.
- e. C-SSRS to be performed after last TMS retreatment session on last day of the retreatment week.
- f. Performed on a subset of subjects at participating sites.
- g. Audiometry assessments must be performed immediately prior to the start of the TMS retreatment and at the completion of the retreatment course.
- Efficacy assessments to be performed the end of each month for monthly visits. Subjects will be called to assess safety and well-being between visits at

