## E. Columbia Suicide Severity Rating Scale:

The Columbia Suicide Severity Rating Scale (C-SSRS) will be used in this study to measure the occurrence of suicidal events and behavior. Assessments are completed prior to baseline, each week during active treatment, and at end of phase.

1) Number of Patients with Suicidal Ideation, Suicidal Behavior, and Self-Injurious Behavior with Suicidal Intent (following the format of Table 1 described in the C-SSRS Rating Guide)

Note: This table will report the proportions of patients between active and sham conditions who report positive response on the suicidal ideation items (1-5), the suicidal behavior items (6-10) by item.

2) Table: Shift Table to Demonstrate Changes in C-SSRS Categories from Baseline During Treatment (following the format of Table 3 of the C-SSRS Rating Guide)

Note: This table will report the proportion of patients between active and sham conditions who report positive response on the suicidal ideation items (1-5), the suicidal behavior items (6-10)

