#### F. Vital Signs:

Vitals were completed before baseline and at the end of each phase. Changes in Height, Weight and Vitals will be provided.

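### Protocol 13.2 puts the C-SSRS on a two-week interval during Phase III retreatment, where protocol 10.2 and SAP 8.E require it weekly

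*Protocol*

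**What the plan says.** The documents give the C-SSRS interval during a Phase III retreatment block in several places.

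- Protocol 13.2, the treatment section: "subjects are assessed every other week with the same efficacy measures used in the Week 6 visit and the C-SSRS".
- Protocol 10.2, Phase III: "The C-SSRS will be completed weekly during TMS retreatment session(s".
- Protocol 8.4, management plan for mania, worsening depression and suicidality: weekly assessments in the active treatment phases, with a pointer to Appendices A to C. The C-SSRS is one of the three instruments named for monitoring.
- Appendix C, footnote e, repeated in the SAP's Phase III schedule: "C-SSRS to be performed after last TMS retreatment session on last day of the retreatment week".
- Footnote c to the same schedule: "Efficacy assessments must be completed every other week during each TMS retreatment". On what precedes a course, it says: "All efficacy and safety assessments must be completed prior to the start of retreatment".
- SAP 8.E: "Assessments are completed prior to baseline, each week during active treatment, and at end of phase".

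Outside retreatment, the C-SSRS row of the Phase III schedule has no mark at any month, including Month 6/ET, in both the protocol and the SAP copies. The list of end-of-six-month assessments in protocol 10.2 also leaves the C-SSRS out.

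**The concern.** Section 13.2 makes the C-SSRS share the interval of the efficacy measures. Every other place that fixes or implies an interval for it during active treatment points to weekly. The likely origin is that two rules, weekly for the C-SSRS and every two weeks for efficacy, were merged into one sentence.

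This matters because 13.2 is the operational section on how retreatment is given and when it stops, so a site could follow it in good faith. The patients concerned are adolescents and young adults whose CGI-S has just worsened by at least one point, confirmed on repeat assessment. The protocol itself treats worsening suicidality as a risk to be watched and as grounds for discontinuation. If sites followed different sections, counts of C-SSRS findings during retreatment would also rest on unequal numbers of ratings.

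**Working it through.** **Step 1. Compare the texts.** No formula applies; the question is which text is the odd one out.

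| Place | C-SSRS during retreatment |
|---|---|
| Protocol 13.2 | Every other week |
| Protocol 10.2, Phase III | Weekly |
| Protocol 8.4, risk section | Weekly assessment in active treatment phases; C-SSRS among the tools |
| Appendix C footnote e, and SAP copy | Last day of the retreatment week; fits weekly but is less explicit |
| Appendix C footnote c, and SAP copy | Every other week for efficacy measures only |
| SAP 8.E | Each week of active treatment |

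Section 13.2 stands alone.

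**Step 2. Count ratings per course.** Inputs:

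- Maximum course length is 6 weeks (protocol 10.1, Phase III).
- A course may end sooner: "TMS should be discontinued when the CGI-S score has returned to the value observed at Phase III entry". The CGI-S is scheduled every two weeks during retreatment, so courses of 2, 4 and 6 weeks are shown.
- Footnote c requires all safety assessments before retreatment starts, and the C-SSRS is listed under safety assessments in that table. This adds one rating under either rule.
- Taper weeks after a course are not counted.

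Formulas, for a course of w weeks: weekly rule, w ratings; 13.2 rule, w/2 ratings; add 1 to each for the pre-retreatment rating.

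| Course length | On treatment: weekly | On treatment: 13.2 | With pre-retreatment rating: weekly | With pre-retreatment rating: 13.2 |
|---|---|---|---|---|
| 6 weeks | 6 | 6/2 = 3 | 6 + 1 = 7 | 3 + 1 = 4 |
| 4 weeks | 4 | 4/2 = 2 | 4 + 1 = 5 | 2 + 1 = 3 |
| 2 weeks | 2 | 2/2 = 1 | 2 + 1 = 3 | 1 + 1 = 2 |

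On-treatment ratings are halved in each case, and the interval between them goes from one week to two.

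**Step 3. Check the end-of-phase wording in SAP 8.E.** Phases I and II have C-SSRS marks through Week 6 and all three taper weeks, so the wording is met there. In Phase III the blank monthly row, its retreatment-only footnote and the 10.2 text agree that the C-SSRS belongs to retreatment. SAP 8.F uses similar wording for vital signs, "Vitals were completed before baseline and at the end of each phase", and vital signs do have a Month 6 mark. A reader of 8.E could therefore expect a Phase III end-of-phase C-SSRS that the schedule does not collect.

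**The case against.** The best defence is that the intent is plain. Weekly appears in the assessment section, the safety-management text and the SAP, and a site rating weekly also satisfies 13.2, because the C-SSRS would then be present at every two-week assessment. That is right about intent, and it means the correction conflicts with nothing else. It does not rescue 13.2, which read alone tells a site that two weeks is enough.

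A reader might infer that a site following 13.2 would leave suicidality unmonitored for two weeks. The documents do not support that. Retreatment is given five days a week; protocol 8.4 has worsening suicidality considered at every treatment visit; protocol 19 describes daily adverse event assessment during the interventional part. What is lost is the structured rating.

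A reader might also infer that the blank monthly row in Phase III is an error. It reads as a deliberate choice, since table, footnote and text agree. There is other coverage: C-SSRS in the taper weeks before Phase III, bi-weekly calls, monthly CGI-S and QIDS-A17-SR, HAMD24/MADRS and CDRS-R at Months 3 and 6, and serious adverse event reporting with narratives. One limit remains: the HAMD suicidality change scores in SAP 9.C are planned for Phase I only.

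Finally, a reader might apply the 36.2% retreatment rate in protocol 8.1 to the expected 37 Phase III entrants to estimate how many would have no Phase III C-SSRS. That rate is a 12-month figure in adults maintained on antidepressants and/or periodic TMS, whereas this trial permits no antidepressants in any phase. It gives no usable estimate here.

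**Conclusion.** The contradiction is real, and protocol 13.2 is the text that is wrong. Its size is 3 against 6 on-treatment ratings in a full course, or 4 against 7 with the pre-retreatment rating. This assumes a 6-week course, a site that follows 13.2 literally, and footnote c read as including the C-SSRS. How many patients are affected depends on the retreatment rate and on which section sites followed; the documents give neither.

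The effect is on safety data collection during retreatment. The two C-SSRS tables in SAP 8.E compare active with sham, Phase III analysis is descriptive (SAP 7.A), and the Phase I efficacy analysis is unaffected.

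The absence of a C-SSRS outside retreatment in Phase III is a design choice. Only the loose end-of-phase wording in SAP 8.E needs attention, as a minor clarification: Phase III C-SSRS data describe retreated patients and should not be presented as covering everyone followed for long-term safety.

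**What to change.** - **Protocol 13.2:** state that the C-SSRS is done weekly during retreatment and that the efficacy measures stay every other week. This is a change to one sentence and adds nothing to what 10.2 already requires.
- **If retreatment has already taken place** (the SAP is dated January 2019 and describes some conduct in the past tense): report the number of C-SSRS ratings obtained per retreatment week, so that courses run on the two-week interval are visible. This costs one descriptive summary.
- **SAP 8.E, minor:** limit the timing sentence to Phases I and II plus retreatment weeks, and describe Phase III C-SSRS results as applying to retreated patients only. This is a text change.
- **Optional:** a C-SSRS at Month 6/ET, if collection is still open. It would add one rating to a visit that already includes HAMD24/MADRS, cognition, vital signs and audiometry.

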13.3 Packaging and Labeling

The NeuroStar XPLOR[®] Therapy System will be clearly labeled with the following warning:

"CAUTION - Investigational Device. Limited by Federal (or United States) law to investigational use"

13.4 Blinding of Study

The blinded TMS coils will arrive from Neuronetics and will be identical in appearance and labeled generically (e.g., Coil X, Coil Y). The device will recognize one coil as active and the other coil as sham. Once a subject has been randomized, the device will "link" the subject's treatment with the corresponding coil. The device will remain inactive if the "incorrect" coil is used for a subject, adding an additional safeguard for each subject and the integrity of the study and allowing the study treaters to remain blinded to the nature of the subject's treatment assignment.

Subjects will be randomly assigned to a coil and will receive all treatments during Phase I of the trial using this coil. Neither the subject nor the study staff (including those administering TMS treatments and those administering mood, cognitive, safety, and imaging assessments) will know whether the subject is

Page 35 of 61

receiving active or sham treatment. Subjects and Parents (if subject < 18 years old or does not meet the local or state legal age requirement) will complete a Pre/Post-Treatment Expectations and Experience Questionnaire (PRE-TEEQ-A/PRE-TEEQ-P and POST-TEEQ-A/POST-TEEQ-P) that queries their initial expectations of trial outcome and final impression of the trial.

In Phase II and III, all treatments will be provided with the known-active coil.

To minimize any source of bias, unblinding of the study will not be done until all subjects have completed all study phases. However, unblinding will occur if the Data and Safety Monitoring Board, consistent with their assigned charter and associated stopping rules, determines that it necessary to do so.

As an additional measure to ensure the integrity of the blinded coil assignment, the study coils at each location may be retrieved by Neuronetics study personnel and new study coils re-assigned.

13.5 Receiving, Storage, Distribution and Return

Receipt of Investigational Devices

NeuroStar XPLOR[®] TMS Therapy System will be delivered to the Investigator and installed by Neuronetics.

Upon receipt of the NeuroStar and study treatment supplies, an inventory will be performed and a device accountability log completed by designated study staff at each site. The designated study staff will count and verify that the shipment contains all the items noted in the shipping invoice. Any discrepancies or damaged or unusable devices in a given shipment will be documented in the device accountability log. The Investigator at each study site will notify Neuronetics immediately of any discrepancies or damaged or unusable products.

Storage

The supplies and disposables required for each treatment will be stored in a supply station separate from clinical practice stock at each site.

Distribution of Study Device

Subjects in Phase I will be randomly assigned to one of the blinded treatment coils at time of enrollment, as outlined in protocol section 13.2. All subjects in Phase II and III will be treated with the known-active, non-blinded therapy coil. All subjects will be treated using a new single-use treatment disposable, or SenStar[®] Treatment Link, from their treatment site at the start of every new treatment. The treatment packs and SenStar Treatment Links will be stored in an area that is separate from clinical practice stock. Regular reconciliation of SenStar Treatment Links received from Neuronetics, SenStars used during study treatments, and SenStars remaining will be performed. This reconciliation of the inventory will be logged in the Device Accountability Log, signed, and dated. Any discrepancies noted will be documented, Neuronetics will be notified, and an investigation will be conducted to determine the cause of the discrepancy. Any SenStars disposed of for any reason other than use for the study will be documented in the Device Accountability Log at the time of disposal.

Return or Destruction of Study Device

The NeuroStar[®] devices purchased from Neuronetics, Inc. will remain at the study sites at the completion of the study. NeuroStar devices and/or XPLORs that are loaned to the study site for purposes of participating in this study will be returned to Neuronetics at conclusion of the study by Neuronetics personnel. SenStars[®] that are remaining in the site study research inventory at the completion of the study will be packaged and returned to Neuronetics.

Page 36 of 61

14 Study Procedures

